C. Study Design flow. Primary care or mental health outpatient clinics agreeing to participate will be randomly selected (N=80 total) and initially offered REP for six months in order to implement LG. Based on previous research and preliminary data, it is expected that after six months of REP at least two-thirds of sites will be non-responsive to REP. The primary focus of the randomized comparisons in this study are sites that are initially non-responsive to REP (k=40), defined based on our preliminary studies as <10 patients receiving LG within six months of initiating REP and that patients received <75% group sessions. (Although not part of the primary randomized comparisons, sites that are responsive at 6 Months will continue to be followed and outcomes will be assessed). The non-responsive sites will be randomized 1:1 to receive additional External Facilitation (**REP+EF**) or External plus Internal Facilitation (**REP+EF/IF**). After another six months (at Month 12), sites that are still non-responsive (based on the same criteria) will be randomized 1:1 to either continue **REP+EF** or augmentation with IF (**REP+EF/IF**). All sites are followed for a total of 24 months. Patient-level outcomes will be assessed by study staff using assessments considered part of routine clinical care (e.g., symptoms and quality of life) starting at the initiation of REP and then at 6, 12, 18, and 24 months later among a pre-selected cohort of n=20 patients per site who are identified by site providers for LG (total patients participating in the project N=k*n=800). Patients receiving Life Goals as part of their routine clinical care may opt in or out in participating in the outcomes assessment component. As with our prior implementation work (R01 MH79994), independent evaluators (study staff who are not aware of the assignment to **REP+EF** or **REP+EF/IF**) will conduct study outcomes assessments to ensure consistency of

data collected across sites and to prohibit provider/site or investigator assessment bias. Pre-identification of LG recipients also maximizes consistency of the patient population across sites (see patient criteria below).

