F. Data Collection and Measures

Data for primary and secondary aims will be collected by study staff from patient surveys, organizational surveys, and provider logs. The assessment package previously developed and implemented by study investigators (R34 MH74509, R01 MH79994) was informed by the RE-AIM framework for evaluating implementation of EBPs. Key measures include patient-level outcomes, LG uptake and fidelity, organizational factors, and REP, EF, and IF activities (Table 3). Data sources include patient-level (surveys), site-level (provider surveys), and project staff logs.

Patient data: Lists of patients and contact information that were identified by the LG providers during the first 3 months of REP (pre-randomization) will be sent to study outcomes assessors who will conduct phone surveys at baseline (after the REP provider training is complete), and 6, 12, 18, and 24 months later. Patient baseline assessments will include assessments already used

in routine clinical care and will be conducted by project staff by phone after the LG provider identifies eligible patients but before the first LG sessions are implemented. Once project staff receive patient lists, they will contact patients, describe the purpose of the study, and ask if the patients would like to participate. Patients will be compensated \$10 for completing each assessment. Patient-level data will be coded with a unique identifier. There will be a crosswalk file that is password protected that is only available to be accessed by study staff that will link unique study ID with a link to the person's identity.

Table 3: Primary and Secondary Assessments – Baseline and Follow-ups

Aims	Measure	Source
1a. Primary outcomes	Health-related quality of life-SF-12 mental health score	Patient survey
1b. Secondary outcomes	Functional impairment-WHO-DAS	Patient survey
	Psychiatric symptoms-PHQ-9, GAD-7, ISS	Patient survey
	LG fidelity and uptake (# sessions, contacts)	LG provider logs, patient surveys
Secondary aims	LG implementation costs (patient, site perspective)	Patient survey, chart review, logs
	REP costs	Study staff logs
	Facilitation costs	Staff, LG provider, Facilitator logs
Covariates	Patient demographic, clinical factors, behaviors use	Patient survey, chart review, logs
	Organizational factors (OTM, ORCA, EBPAS)	Site leader, provider surveys

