Intent-to-treat. Every effort will be made to collect patient level outcomes across all 80 sites and patients (N=1600) to conduct the primary and exploratory analyses (see below). The 40 sites randomized at month 6 (total 800 patients) will be included in the intent-to-treat randomized sample. The Primary Aim analysis will compare strategies in non-responding sites (k=40) beginning with **REP+EF/IF** versus strategies beginning with **REP+EF** on longitudinal change in patient-level SF-12 mental health scores (MCS- primary outcome). This analysis is a comparison of cells A+B+C vs. D+E (Figure 2). For this analysis, the longitudinal outcome is SF-12 mental health scores measured at Months 6 (pre-randomization), 12, 18, and 24. The primary contrast is the between groups difference in change from Month 6 to Month 18. The follow-up contrast at Month 24 will also be examined in this and all subsequent analyses. Linear mixed models (LMM), also known as random effects models, fit with SAS PROC MIXED will be used to analyze the longitudinal data. LMMs use all available measurements, allowing subjects to have an unequal number of longitudinal observations and producing unbiased parameter estimates as long as unobserved values are missing at random. The analysis will fit a 3-level (repeated measures for each person clustered within site) LMM with fixed effects for the intercept, time, group, and a group-by-time interaction term, where group is an indicator of **REP+EF/IF** vs. **REP+EF**. The LMM will also include random effects for site and time, an unstructured within-person correlation structure for the residual errors, and it will adjust for the following pre-randomization measures collected through Month 6: state and type of practice (primary care- or mental health site). Model diagnostics will be used to determine the suitability of more parsimonious (e.g., autoregressive) correlation structures, and nonlinear (e.g., piecewise linear or quadratic) effects for time. LMMs similar to the above for the primary outcome will be conducted for the secondary outcomes: **REP+EF/IF** vs. **REP+EF** on change in number of LG encounters, functional impairment, and psychiatric symptoms.

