The goal of the Secondary Aim 1 analysis is to determine whether continuing **REP+EF** versus augmenting with **REP+EF/IF** leads to changes in outcomes, among sites who are non-responsive at Month 12. This analysis is a comparison of cells B vs. C (Figure 2). Both primary and secondary longitudinal outcomes above will be examined using an LMM similar to that described above, except (a) including only the subset of sites that do not respond at Month 12 to **REP+EF**, (b) using monthly longitudinal outcomes from Month 12 to Month 24, and (c) the LMM will use dummy-indicators for time (i.e., time-saturated model since there are only 3 measurement times for each longitudinal outcome).

The Secondary Aim 2 analysis will involve an analysis of implementation costs. The implementation (REP, EF, IF) costs will be summed for each site as a measure of total costs and changes in costs will also be assessed over time (6, 12, 18, 24 months). An exploratory analysis of the incremental effectiveness of IF by comparing costs from sites given **REP+EF/IF** versus those with **REP+EF** will be conducted from the site's perspective. In regression models of costs, Generalized Linear Models with log link functions will be used to correct for heteroscedasticity and reduce the impact of outliers. Effectiveness will be measured by changes in health utilities using the SF-6 (a subset of SF-12 questions) as well as the Euro-QOL 5D. Cost-effectiveness will be calculated as the ratio of incremental average site-level cost and incremental average effectiveness (change in patient-level utilities) of IF. A standard nonparametric bootstrapping approach will be used to calculate confidence intervals and cost-effectiveness acceptability curves.

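### The primary mixed model leaves out the SF-12 MCS collected at REP initiation, a second pre-randomisation value that could add precision at almost no cost

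*Combined protocol and SAP*

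**What the plan says.** Section V.C (Study Design flow) plans patient outcomes "starting at the initiation of REP and then at 6, 12, 18, and 24 months later among a pre-selected cohort of n=20 patients per site". Section V.F (Patient data) agrees: lists of patients go to assessors "who will conduct phone surveys at baseline (after the REP provider training is complete), and 6, 12, 18, and 24 months later". The two places describe the first survey slightly differently, but on either description it precedes the Month 6 randomisation. Section V.C also makes taking part in the assessments the patient's choice.

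Section VI (Intent-to-treat) defines the primary analysis on a shorter series: "the longitudinal outcome is SF-12 mental health scores measured at Months 6 (pre-randomization), 12, 18, and 24". From those four visits, the plan takes as its main comparison the arm difference in how MCS changes over the twelve months after randomisation, that is, up to Month 18. The mixed model has "fixed effects for the intercept, time, group, and a group-by-time interaction term" and adjusts for "pre-randomization measures collected through Month 6: state and type of practice". Month 0 MCS appears in none of these lists. Non-linear time is left to model diagnostics.

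Secondary Aim 1 compares the sites re-randomised at Month 12, "using monthly longitudinal outcomes from Month 12 to Month 24", with indicator variables for the three measurement times. The MCS values from Months 0 and 6 are not used.

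Section V.D includes the site mean of mental health quality of life at Month 6 among the balancing factors for the first randomisation.

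**The concern.** Both Month 0 and Month 6 precede the first allocation, so the plan collects the primary outcome twice before randomisation and uses it once. A change from a single pre-randomisation visit carries that visit's measurement noise. A second value from the same patients can reduce that noise without threatening validity, because allocation cannot have affected it. It also brings in patients who have a Month 0 survey but miss Month 6, and it makes the missing-at-random assumption easier to defend, since dropout may then depend on Month 0 MCS.

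What is at stake is precision. Only 40 sites are randomised. Secondary Aim 1 draws on the non-responders within one arm of about 20 sites. The data are to be collected in any case, and the documents give no reason for leaving them out.

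**Working it through.** **Inputs from the documents.** Visits at Months 0, 6, 12, 18 and 24 (V.C, V.F); model visits 6, 12, 18 and 24 (VI); 40 sites randomised 1:1. The plan states no power, SD, ICC or visit correlation for this contrast, so there is no precision figure to reproduce. The counts agree: 40 × 20 = 800 and 80 × 20 = 1,600.

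**Assumptions.** Unit variance at each visit, the same correlation pattern at patient and site level, complete data and no random slopes. Three patterns are used: exchangeable; AR(1); and partly decaying, with correlations 0.50, 0.425 and 0.3725 at 6, 12 and 18 months apart.

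**Method.** Apply generalised least squares to the arm differences d0, d6, d12, d18, d24, with variance c'(X'V⁻¹X)⁻¹c. Write r for the correlation between Months 6 and 18.

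*Visit indicators.*
- Free offset at Month 6 (plan): 2(1 − r). Exchangeable 0.5: 1.000. AR(1) 0.5 (r = 0.25): 1.500.
- Month 0 shares the offset: the minimum over w of Var[d18 − w·d6 − (1 − w)·d0]. Exchangeable: 1.5(1 − ρ) = 0.750 at ρ = 0.5. AR(1) 0.5: 1.75 + w² − 1.25w, least at w = 0.625, giving 1.359.
- Arms equal at Month 6 only: 1 − r². Exchangeable 0.5: 0.750.
- Arms equal at Months 0 and 6, exchangeable: 1 − 2ρ²/(1 + ρ) = 0.667 at ρ = 0.5.

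*Linear time from Month 6.* With times 0, 1, 2, 3 in six-month units the sum of squares is 5, so the 12-month contrast has exchangeable variance 4(1 − ρ)/5 = 0.400 at ρ = 0.5. Placing Month 0 at time 0 with its own mean gives times 0, 0, 1, 2, 3 and a sum of squares of 6.8: 4 × 0.5/6.8 = 0.294. The ratio is 5/6.8 = 0.74 for any ρ.

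| Correlation | Time | Free offset | Offset shared with Month 0 | Ratio | Equal at Month 6 | Equal at Months 0 and 6 | Ratio |
|---|---|---|---|---|---|---|---|
| Exchangeable 0.5 | indicators | 1.000 | 0.750 | 0.75 | 0.750 | 0.667 | 0.89 |
| Exchangeable 0.5 | linear | 0.400 | 0.294 | 0.74 | 0.294 | 0.250 | 0.85 |
| Exchangeable 0.7 | indicators | 0.600 | 0.450 | 0.75 | 0.510 | 0.424 | 0.83 |
| Exchangeable 0.7 | linear | 0.240 | 0.176 | 0.74 | 0.204 | 0.163 | 0.80 |
| Partly decaying | indicators | 1.150 | 0.950 | 0.83 | 0.819 | 0.785 | 0.96 |
| AR(1) 0.5 | indicators | 1.500 | 1.359 | 0.91 | 0.938 | 0.938 | 1.00 |
| AR(1) 0.5 | linear | 0.774 | 0.689 | 0.89 | 0.414 | 0.414 | 1.00 |
| AR(1) 0.7 | indicators | 1.020 | 0.981 | 0.96 | 0.760 | 0.760 | 1.00 |
| AR(1) 0.7 | linear | 0.584 | 0.555 | 0.95 | 0.389 | 0.389 | 1.00 |

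**What does not help.** With visit indicators and complete data, Month 0 added as an unconstrained visit gives a ratio of 1.000 in every scenario. With 10-30% of visits missing at random the ratio is 0.98-1.00. A time-constant main effect of Month 0 MCS cancels from a change contrast.

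**Clustering.** With 20 versus 20 sites, 20 patients per site, assumed ICC 0.01 or 0.05 and site autocorrelation 0.5 or 0.8, the shared-offset ratio under linear time is 0.74-0.96. The extra reduction from Month 0 once the arms are equal at Month 6 is 0-18% (indicators) or 0-21% (linear).

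**Secondary Aim 1.** With k pre-randomisation visits, equal arm means and exchangeable correlation, the variance is 1 − kρ²/(1 + (k − 1)ρ). At ρ = 0.5, k = 1 gives 0.750 and k = 3 gives 0.625, a ratio of 0.83. Under AR(1) the ratio is 1.00.

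**The case against.** The strongest reply has four parts.

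1. *Form of time.* The fixed effects read most naturally as linear time, especially since Secondary Aim 1 names time indicators as a departure from the primary model. A reader might infer that the primary contrast rests on one noisy reference visit. Under linear time it does not: it draws on all four visits. Requiring visit indicators would then lose precision. For exchangeable 0.5 the variance would rise from 0.400 to 0.750 or 0.667; for AR(1) 0.5, from 0.774 to 1.359 or 0.938. This stands, so the remedy must not impose indicators. The shared-offset gain survives under linear time (ratios 0.74-0.95 in the table).

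2. *The constraint does much of the work.* Constraining Month 6 alone often gains as much as sharing the offset with Month 0, or more. This also stands. But the plan has only the Month 6 data, not the constraint: its group term leaves the arms free there.

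3. *Balancing on Month 6.* Allocation on site-mean Month 6 quality of life already shrinks d6. In the limit d6 = 0, with visit indicators and exchangeable 0.5, the planned contrast has true variance 0.750 and the shared offset gives 0.687, a gain of 8% rather than 25%. Under AR(1) 0.5 the shared offset does worse (0.938 to 1.043). Equal arm means at both visits give 0.667 and 0.938, because that residual does not depend on d6 or d0. Real balance will be partial, and model-based standard errors would not show it, but the headline gain is overstated to that extent.

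4. *Validity.* Starting the series at the randomisation visit is legitimate. A reader might infer bias or an analysis error; the documents support neither.

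A reader might also suppose that every cohort patient will have a Month 0 value. Collection is planned, but assessment is voluntary and no completion rate is given.

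**Conclusion.** The point holds as one of efficiency. Month 0 MCS is planned, precedes randomisation, and is unused in the primary model; Secondary Aim 1 likewise leaves out two earlier values. Relative to arms left free at Month 6, sharing the offset with Month 0 reduces variance by about 4% (AR(1) 0.7, visit indicators) to 26% (exchangeable, linear time). If the arms are already equal at Month 6, Month 0 itself contributes 0% (AR(1)) to about 20% (exchangeable 0.7, linear time).

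These are model-based ranges under assumed correlations. Balancing on Month 6 quality of life makes the realised gain smaller, so the upper end should not be read as the expected benefit. The change is still worth specifying in advance, because it needs no new data and would look selective if added after results are seen.

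**What to change.** In Section VI, primary analysis:

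- Add Month 0 MCS to the outcome series as a pre-randomisation visit with its own time mean and no separate arm effect. Preferably constrain arm means equal at Months 0 and 6; at the least, let Month 0 share the Month 6 arm offset.
- State the form of time and keep it from Month 6 onward; visit indicators are not required. Keep the REP run-in out of the group-by-time slope, for example by setting the time variable to zero at both Months 0 and 6 and adding an indicator for Month 0.
- Keep the primary contrast as the arm difference in change to Month 18.
- Do not add Month 0 only as an unconstrained visit or as a time-constant main effect.

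In Secondary Aim 1, treat Months 0 and 6 in the same way, as visits before the Month 12 re-randomisation. Apply the same approach to the secondary patient-survey outcomes.

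The cost is a change of SAP wording, one or two more mean parameters and a larger covariance matrix. No patients or surveys are added. There may be no gain if correlations decay as AR(1) and the arms are already constrained equal at Month 6.

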D. Site Organizational Randomization: The unit of randomization is the site and will be stratified using a minimization allocation method. This procedure will ensure that groups are balanced for site variables that may correlate highly with outcomes. The Month 6 randomization for REP non-responsive sites, will be stratified by state, type of practice (primary care or mental health site), and site-aggregated mean mental health related quality of life measured at Month 6. The Month 12 randomization for non-responders to **REP+EF** will be stratified by site-aggregated quality of life measured at Month 12. Based on interviews with site leaders and the literature, participating sites differ more by state and practice type than by type of network, and state and practice are correlated with mental health related quality of life and number of LG encounters.

E. Implementation Components (Table 1)

REP: All sites will receive REP (Table 1) in the first three months and will be monitored monthly up to the sixth month in the use of LG. REP includes dissemination of the LG package, training, and LG uptake monitoring for up to six months. REP includes an off-site trainer, which is neither an External nor Internal Facilitator. The following REP components were previously operationalized by study investigators (R01 MH79994):

Step 1: Dissemination of LG package, in-service, and patient selection: Each site will designate at least one provider with a mental health background (master’s in social work, nursing degree, or bachelor’s with two years’ experience in mental health psychosocial treatment) to implement LG (“LG provider”). Regional two-hour in-services will be provided by study investigators who will give an overview of LG including the evidence, and details on how to implement LG in their setting. During the in-service, the LG package will be disseminated and the REP trainer will coach the LG providers in pre-identifying a cohort of patients.

Table 1: Summary of REP, REP+EF, and REP+EF/IF Implementation and Fidelity Measures

Implementation Component	REP	REP+EF	REP+EF/IF
REP (REP)	All sites	Randomize to Non-Responding Sites	Randomize to Non-Responding Sites
Step 1: Disseminate package: LG in-service and identify appropriate patients using medical record review	√	√	√
Step 2: Train site providers in LG	√	√	√
Step 3: Monitor LG uptake via monthly reporting sheets	√	√	√
REP+External Facilitator (REP+EF)			

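### The primary model gives pre-randomisation Month 6 MCS its own free arm difference, so the Month 6-to-18 contrast is valid but somewhat less efficient, and mildly conservative under the planned minimisation

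*Combined protocol and SAP*

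**What the plan says.** Section VI (Analyses and Evaluation, Intent-to-treat) defines the primary response as "SF-12 mental health scores measured at Months 6 (pre-randomization), 12, 18, and 24" and the primary contrast as the arm difference in change from Month 6 to Month 18. The model has "fixed effects for the intercept, time, group, and a group-by-time interaction term", together with "random effects for site and time" and an unstructured within-person residual covariance. On covariates, "it will adjust for the following pre-randomization measures collected through Month 6: state and type of practice".

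Section V.D (Site Organizational Randomization) says that allocation of sites "will be stratified using a minimization allocation method". For the Month 6 randomisation the factors are state, practice type "and site-aggregated mean mental health related quality of life measured at Month 6".

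No section constrains the two arms to a common Month 6 mean or uses Month 6 MCS as a covariate. The coding of time is not stated.

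**The concern.** Month 6 MCS cannot be affected by the allocation that follows it. With a group term and a group-by-time term, the model still estimates a Month 6 arm difference and in effect subtracts it in full from the later difference. When the correlation between Month 6 and Month 18 is below 1, this carries baseline noise into the contrast.

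Minimisation on the Month 6 site mean changes how the cost appears. It makes the arms more alike at Month 6 than chance would, so the change estimate is steadier than under simple allocation. The free-baseline model does not know this, and its standard error is computed as if the Month 6 difference varied freely. The loss therefore shows mainly as an overstated standard error and a slightly conservative test.

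At stake is some power in a comparison that rests on 40 sites.

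**Working it through.** **Inputs from the documents.** 40 randomised sites, 1:1, so 20 per arm; 20 patients per site (40 × 20 = 800, as stated); visits at Months 6, 12, 18 and 24. There is no power calculation to reproduce.

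**Assumed inputs.** SD 10; ICC 0.01 to 0.10; correlation of site effects between visits 0.8 to 0.95; within-patient correlation 0.5 to 0.7; SD of a random site slope 0, 0.5 or 1.0 per visit; complete data.

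**Step 1. Worked case, no balancing on Month 6.** ICC 0.05, site correlation 0.8, patient correlation 0.5, no site slope.

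- Variance of a site mean: 5 + 95/20 = 9.75.
- Covariance between Months 6 and 18: 0.8 × 5 + 0.5 × 95/20 = 6.375, so r = 6.375/9.75 = 0.654.
- Planned model, categorical time: variance = (2/20) × 2 × (9.75 − 6.375) = 0.675; SE 0.822.
- Common Month 6 mean: variance = (2/20) × 9.75 × (1 − r²) = 0.558; SE 0.747.
- Loss: 1 − 0.558/0.675 = 17.3%, which equals (1 − r)/2.
- Linear time: SE 0.520 against 0.472, a loss of 17.4%.

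The shortcut (1 − r)/2 needs equal variances at Months 6 and 18. With slope SD 1.0 in this case it gives 22.5%, against an actual 10.9% for categorical time.

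**Step 2. Grid of 72 settings, still without balancing on Month 6.** Loss of variance by generalised least squares:

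| Site slope SD | Linear time | Categorical time |
|---|---|---|
| 0 | 6.0–23.4% | 6.4–22.5% |
| 0.5 | 3.6–15.9% | 5.0–18.9% |
| 1.0 | 1.6–8.2% | 3.1–12.9% |

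The loss is below 15% in 63 of 72 settings (linear) and 60 of 72 (categorical). Lower site correlations, or correlations that decay over time, give larger losses. This grid shows the mechanism, but it does not describe the planned allocation.

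**Step 3. Simulation with and without minimisation.** Four visits, linear time, site intercept and slope, 40 sites, variances by REML, t with 38 df (assumed), 2,500 runs per setting (Monte Carlo error about 0.4 points on size). Four data settings (ICC, site correlation, patient correlation, slope SD): (0.05, 0.8, 0.5, 0), (0.05, 0.8, 0.5, 0.5), (0.05, 0.8, 0.5, 1.0) and (0.10, 0.95, 0.7, 0.5). The effect was set so that the constrained model has about 80% power. The simulation uses a site-mean form of the three-level model, not PROC MIXED itself.

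| | Minimised on Month 6 site mean | Simple 1:1 |
|---|---|---|
| Size, planned model | 3.5–5.1% | 4.7–5.6% |
| Variance ratio constrained/planned, true | 0.92–0.99 | 0.84–0.98 |
| Variance ratio constrained/planned, reported | 0.82–0.96 | 0.83–0.96 |

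Under minimisation the constrained model has size 4.2–5.6%. Power is 72.6–78.7% planned against 76.9–81.1% constrained, a gain of 0.9 to 7.6 points. The true ratio moves towards 1 under minimisation while the reported ratio hardly changes, which is the overstated standard error. A simpler site-mean simulation under minimisation gave size of about 3.6–4.6% for the change contrast and 4 to 11 points less power than adjusting for Month 6, so the upper end depends on the settings chosen.

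**Step 4. Would listing the third minimisation factor help?** The Month 6 site mean was added as a time-constant covariate beside state and practice type, with Month 6 still a response. In one check the contrast and its variance were 0.370 and 0.775 with and without it. In another, at correlation 0.5, the variance was 0.0992 with and without it, against 0.0743 for the constrained model. A covariate that shifts every visit equally cancels from a change.

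**Step 5. Time coding.** If the group term is simply dropped while linear time runs in study months, equality is forced at Month 0 instead of Month 6. Over the 72 settings the expected contrast is then 72 to 94% of the true effect.

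**The case against.** The strongest reply is that a freely estimated baseline in a longitudinal mixed model is a standard and valid choice. Month 6 MCS is not ignored, since it is in the likelihood and its site mean drives the allocation. With minimisation the true variance penalty is only 1 to 8%. All of this stands, and it is why the point concerns efficiency only.

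The reply also notes that the constraint needs a cohort fixed before randomisation. Sections V.C and V.F describe such a cohort. Two parts of section V.E, on identifying the target population and on describing Life Goals, tie assessment to patients who receive Life Goals. Non-responsive sites have few recipients at Month 6, so under that reading some patients could enter after randomisation, and forcing equal Month 6 means could then introduce bias. This also stands, as a condition on the fix.

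A reader might infer four stronger claims that the documents do not support:

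- *The analysis is biased or invalid.* It is a sound randomised comparison.
- *Omitting the third minimisation factor from the covariate list is a separate fault.* Step 4 shows that listing it changes nothing. The conservatism comes from minimisation combined with a free-baseline change contrast.
- *Up to 23% of variance is lost.* That figure assumes no balancing on Month 6, whereas section V.D specifies it.
- *The same loss applies elsewhere.* Section VI says "LMMs similar to the above for the primary outcome will be conducted for the secondary outcomes", but no loss was calculated for those outcomes. For Life Goals encounters, sites are selected for low uptake at Month 6, which restricts the baseline range. For Secondary Aim 1, whose randomisation "will be stratified by site-aggregated quality of life measured at Month 12", adjusting changed power by −3.5 to +5.4 points with 8 to 20 sites (an assumed range), so no reliable gain is shown.

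**Conclusion.** The point holds for the primary outcome as a modest loss of efficiency. Under the planned minimisation the estimate is slightly noisier than necessary, the reported standard error is somewhat too large, and the test is mildly conservative in some settings and close to nominal in others. The cost is about 1 to 8 points of power in the four settings of the main simulation.

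The direction is secure. The size is not, because the documents give no SD, ICC, correlation, minimisation probability, degrees-of-freedom method or target effect, and the simulations assume complete data. The change is worth making because it is nearly free, but the planned analysis would remain defensible without it.

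**What to change.** For the primary outcome, in this order:

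1. Reconcile sections V.C and V.F (cohort identified in advance) with the two parts of section V.E (patients receiving Life Goals) on who is assessed. Apply the constraint to the cohort identified before randomisation.
2. Constrain the two arms to a common Month 6 mean. Code time as zero at Month 6, or as categorical with Month 6 as the reference, and state which.
3. Keep a site slope or a more general site covariance. In a categorical-time check, a constrained model that omitted a real site slope had size of up to 6.1%. Keep state and practice type.

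An alternative is to model Months 12 to 24 with each patient's Month 6 MCS and the Month 6 site mean as covariates. Patients missing Month 6 would then drop out unless their values are imputed, so the constrained model is preferable. For the secondary outcomes, the same use of each outcome's own Month 6 value is optional.

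The cost is a few sentences in the analysis plan. No new data are needed, because Month 6 MCS is already collected before randomisation and its site mean is already used in the allocation.

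### As specified, adjustment for state and practice type barely touches the Month 6-to-18 change contrast; covariate-by-time terms would make it effective

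*Combined protocol and SAP*

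**What the plan says.** Section VI (Intent-to-treat) defines the primary analysis as a linear mixed model in which "the longitudinal outcome is SF-12 mental health scores measured at Months 6 (pre-randomization), 12, 18, and 24". The fixed part has "fixed effects for the intercept, time, group, and a group-by-time interaction term", and the covariance part has "random effects for site and time, an unstructured within-person correlation structure for the residual errors". On covariates, "it will adjust for the following pre-randomization measures collected through Month 6: state and type of practice". The section allows nonlinear time and simpler correlation structures after diagnostics, but it neither lists nor rules out an interaction of state or practice type with time. The target is stated plainly: "The primary contrast is the between groups difference in change from Month 6 to Month 18". Similar models are planned for the secondary outcomes.

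Section V.D minimises the Month 6 allocation on state, practice type and the site mean of mental health quality of life. It gives as a reason that "state and practice are correlated with mental health related quality of life and number of LG encounters".

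**The concern.** Factors used to balance an allocation should normally be in the analysis in a form that acts on the estimate. Here the estimate is a change, while the covariates appear to act only on level. If sites in different states or practice types improve at different rates, two things follow. Where minimisation has balanced the factors, the standard error still carries variation that the design has removed, so the interval is too wide and the test conservative. Where imbalance remains, its effect on change stays in the estimate. Either way, a result reported as adjusted for state and practice type would be adjusted for them hardly at all.

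**Working it through.** The documents give no SD, ICC, dropout rate, alpha or power for this analysis, so there is no planned figure to reproduce. From the documents come 40 sites allocated 1:1, 20 patients per site (40 × 20 = 800), outcomes at Months 6, 12, 18 and 24, three states and two practice types. Every variance, covariate effect and dropout rate below is an assumption.

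**1. Why the main effects cancel.** With complete data and equal sites, each site's vector of four visit means, Y, has a common covariance matrix S. A time-constant covariate adds the same amount to all four elements. Split Y into the weighted mean W = 1'S⁻¹Y / 1'S⁻¹1 and contrasts C'Y with C'1 = 0.

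- Cov(C'Y, W) = C'SS⁻¹1 / (1'S⁻¹1) = C'1 / (1'S⁻¹1) = 0.
- The covariate effect appears only in W, since C'1 = 0.
- W has its own free intercept and group terms, so it carries no information on the change parameters.

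The change contrast is therefore estimated from C'Y alone, and the covariates drop out of both the estimate and its SE.

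**2. Numerical check, complete data.** Generalised least squares with known covariance. Assumed: residual SD 10, within-person correlations 0.4-0.6, site intercept variance 5, site slope variance 0.5 per 6 months, state effects +3 and −3, practice effect 5 points, true contrast 1.5. With and without the main effects the contrasts agreed to about 2 × 10⁻¹⁴. The SEs were identical: 0.8367 with visit indicators and 0.6749 with linear time. This held with imbalanced covariates and, in the visit-indicator fit, when practice type had its own trend.

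The first SE can be had by hand, taking the Month 6-18 correlation as 0.5. The variance of a site's mean change is 0.5 × 2² + 2 × 100 × (1 − 0.5)/20 = 2 + 5 = 7, so SE = √(7 × (1/20 + 1/20)) = √0.7 = 0.8367. No covariate term enters.

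**3. Incomplete data and unequal sites** (same assumptions, visit indicators):

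| Situation | Effect of main effects on the contrast |
|---|---|
| Site sizes 10-20, complete data | at most 0.07 points |
| 10/20/30% dropout by Month 18, completely at random | at most about 0.06 points |
| 10/20/30% dropout depending on practice type, differently by arm | mean shift 0.034 / 0.080 / 0.143 points |

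The last row is 0.034/0.859 = 4%, 0.080/0.886 = 9% and 0.143/0.921 = 16% of the SE. Precision hardly moved in any run: in that row at 30% dropout, the SE was 0.9208 without the covariates and 0.9212 with them.

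**4. Size if the factors predict change.** Let ICC be the site ICC of change and f the share of site-level variation in change explained by state and practice type. Under balanced allocation, the ratio of reported to true SE is

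r = √{ [ICC + (1 − ICC)/20] / [(1 − f)·ICC + (1 − ICC)/20] }.

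SD and within-person correlation cancel from r.

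| f | ICC 0.02 | ICC 0.10 |
|---|---|---|
| 0% | 0% | 0% |
| 5% | √(0.069/0.068): 0.7% | √(0.145/0.140): 1.8% |
| 20% | √(0.069/0.065): 3.0% | √(0.145/0.125): 7.7% |
| 60% | √(0.069/0.057): 10.0% | √(0.145/0.085): 30.6% |

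For a nominal 5% test, the normal approximation 2Φ(−1.96r) gives a true type I error of 4.3% at r = 1.030 and 1.0% at r = 1.306.

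**5. Residual imbalance.** With complete data and covariates imbalanced by chance, adding the covariate-by-time terms moved the estimate by an SD of 0.21 points when practice type had no trend. The SD was 0.41 points when practice type drifted by an assumed 1 point per 6 months (SE 0.84 in both). With exact balance the move was close to 0. Minimisation should put the trial nearer that end.

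**The case against.** Three stronger readings are tempting, and the documents support none of them.

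A reader might infer that the planned adjustment does nothing to the primary result. That is exact only for complete data and equal sites. Section V.E has assessors follow up to 20 patients per site, and section VI expects gaps: "LMMs use all available measurements, allowing subjects to have an unequal number of longitudinal observations", with the model "producing unbiased parameter estimates as long as unobserved values are missing at random". Whether data are missing at random depends on what the model conditions on, and state and practice type are part of that. In a run with 30% dropout depending on practice type, arm and the previous score, the contrast averaged 1.35 without the main effects and 1.50 with them, against a true 1.50. With 200 replicates, each average has a Monte Carlo error of about 0.92/√200 = 0.065, but the paired shift of 0.15 is well determined. The main effects have a use and should stay.

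A reader might infer that the plan confines the factors to main effects. It does not say so; that follows from the listed terms. If interactions with time are intended, the plan needs to state them.

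A reader might infer that the SE is known to be too wide. Section V.D links the factors to quality of life and to the number of encounters, not to change in either, and main effects do model level. If the factors explain none of the site-level variation in change, there is no inflation. The same caution applies to the secondary outcomes.

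It is also fair to say that the two harms pull against each other. The SE is too wide to the extent that minimisation balanced the factors, and imbalance remains to the extent that it did not. Both cannot be large together.

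What stands is that, as listed, the model cannot account for differing change by its own allocation factors, and incomplete data do not restore the missing precision.

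**Conclusion.** The point holds in a limited form. On the natural reading of section VI, adjusting for state and practice type has no effect on the Month 6-to-18 contrast with complete data and equal sites, and little otherwise. The largest average shift in the dropout runs set out under step 3 was 16% of the SE, under a deliberately unfavourable pattern. Precision is essentially unchanged throughout.

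The consequence is conditional. Under an assumed ICC of change of 0.02-0.10 and balanced allocation, the SE excess is zero at a 0% share, about 1-2% at 5%, and 3-31% at 20-60%. Nothing in the documents says where in that range the trial lies. The SE error is in the conservative direction, so the type I error is not inflated by it; what may be lost is precision. This is a cheap improvement, not a flaw that invalidates the comparison. The cancellation is algebra. The sizes rest on assumed variances and dropout and, in the fitted runs, on a covariance treated as known.

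**What to change.** In section VI, state that the primary model includes state-by-time and practice-type-by-time terms as well as the two main effects, and that the similar models for the Month 6 randomised comparison do the same. Code time for these terms as in the rest of the model, and leave the group contrast as defined.

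State has two free parameters and practice type one, so the cost is 3 parameters with linear time, or 3 × 3 = 9 with visit indicators. For the change contrast, roughly 40 − 2 = 38 site-level degrees of freedom become 38 − 3 = 35, and the 5% critical value goes from 2.024 to 2.030. If the factors do not predict change, that small loss brings no gain. The wording should be fixed before outcome data are seen by arm.
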